## PROTOCOL SYNOPSIS

Title	A Randomized, Double-Blind, Vehicle-Controlled Study To Evaluate The Safety And Efficacy Of 146-9251 Cream Applied Twice-Daily For Six Weeks In Subjects With Ichthyosis Vulgaris
Study Type	Phase 2
Test Articles	1. 146-9251 Cream (Crown Laboratories) 2. Vehicle Cream
Study Objective	The objective of this study is to determine and compare the safety and efficacy of topical 146-9251 Cream and vehicle cream applied twice daily for up to 6 weeks in subjects with moderate to severe ichthyosis vulgaris (IV).
Study Design	Double-blind, randomized, multicenter, vehicle-controlled study.
Treatment Groups	Eligible subjects will be randomized (1:1) to one of two treatment groups: 1. 146-9251 Cream 2. Vehicle cream The assigned test article will be applied by the subjects twice daily for up to 6 weeks.
Duration of Treatment	Up to 6 weeks
Duration of Study	Up to 6 weeks for an individual subject
Study Population	Male or female subjects at least 12 years of age with moderate to severe IV.
Total Number of Subjects	Approximately 88 subjects will be enrolled (44 per treatment arm).
Number of Sites	Approximately 5 sites will participate in the study.
Inclusion Criteria	To enter the study, a subject must meet the following criteria:  1. Subject is a male or female and is at least 12 years of age at the time of enrollment. 2. Subject has provided written informed consent/assent. A subject under 18 years of age must provide written informed assent and be accompanied by the parent or legal guardian at the time of assent/consent signing. The parent or legal guardian must provide informed consent for the subject. If a subject becomes 18 years of age during the study, the subject must provide written informed consent at that time to continue study participation. 3. Subject and parent/guardian (if applicable) are willing and able to apply the test article(s) as directed, comply with study instructions, and commit to all follow-up visits for the duration of the study. 4. Subject has a clinical diagnosis of IV involving a minimum of 5% body surface area (BSA) within the Treatment Area.  The Treatment Area is defined as the entire body exclusive of the a) head and neck and b) mucosal areas.

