	
1. Visit 1 (Day 1) - Screening/Baseline Visit: At Visit 1, study staff will explain the study procedures and an informed consent/assent must be signed prior to the initiation of any study-related procedures. At this visit, consenting/assenting subjects will have their medical history and demographics, concomitant medications and procedures/therapies, and inclusion/exclusion (I/E) criteria reviewed to determine subject eligibility. Subjects that require a “washout” period prior to enrollment into the treatment phase to meet I/E criteria requirements will be required to return to the clinic within 45 days to complete the remaining activities. Subjects who require “washout” for longer than 45 days will be re-consented. All WOCBP must have a negative UPT. A brief physical exam, vital signs (including height, and weight), clinical laboratory testing, photography, which is optional, at select site(s) per a photo guide provided by the Sponsor, and clinical evaluations will be performed prior to test article application. The Treatment Area will be defined as the entire body exclusive of a) the head and neck and b) mucosal areas*. The location of the IV to be treated and the percent BSA with IV in the Treatment Area will be recorded prior to test article application. Subjects who meet all inclusion criteria and no exclusion criteria will be randomized and assigned to the next available (lowest) subject number in ascending order. The test article will be weighed prior to dispensing to subjects. Test article, Subject Instruction Sheet, and Subject Diary with completion instructions will be dispensed. At this visit, study personnel will review the Subject Instruction Sheet and the subject and parent/guardian (if applicable) will be instructed on how and where to dispense and apply test article to all affected skin in the Treatment Area and to record applications in the Subject Diary. Subjects will apply the first dose of the assigned test article to all affected skin in the Treatment Area under staff supervision. Any adverse events (AEs) post-application will be recorded. Subjects will apply the assigned test article to all affected skin in the Treatment Area twice daily for up to 6 weeks. The subject will then be scheduled for Visit 2.
 
* Note disease on the neck and face if present may be treated with a bland moisturizer, but shall not be evaluated.
 
2. Visit 2 (Week 2, Day 15 ± 2) and Visit 3 (Week 4, Day 29 ± 2): Subjects enrolled into the study will return to the clinic at Weeks 2 and 4 for the study staff to perform the clinical evaluations, record percent BSA with IV in the Treatment Area, collect, review and dispense a new Subject Diary for test article compliance, update concomitant medications and procedures/therapies, record AEs, collect and weigh used test article and dispense test article if necessary. Photography, which is optional, will be performed at select site(s) per a photo guide provided by the Sponsor. Subjects whose IV is completely clear (IGA score = 0 and all clinical signs of IV = 0 [scaling = 0, fissuring = 0, and erythema = 0]) at Day 15 or Day 29 will complete the end of study (EOS) procedures. These subjects will have completed the study. Subjects whose IV is NOT completely clear will be instructed to continue twice daily treatment until the next visit and to record all applications in the Subject Diary. The subject will be scheduled for the next visit.
 
3. Visit 4 (Week 6, Day 43 ± 3 [OR Day 15 ± 2 or Day 29 ± 2 for subjects who are clear]) – End of Treatment/End of Study or Early Discontinuation: These activities may occur as scheduled at the end of the 43-day treatment period or earlier if (a) the subject is to be dropped from the study or (b) the subject’s IV within the Treatment Area is completely clear at Day 15 or Day 29. At this visit, the study staff will perform the clinical evaluations, record percent BSA

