Study Endpoints	
Efficacy Endpoint(s): IGA scores and the clinical signs and symptoms of IV will be dichotomized to "treatment success" or "treatment failure" where "treatment success" is defined as at least a two grade decrease in severity score relative to Baseline. Dichotomization of scores for clinical signs and symptoms of IV will exclude subjects with Baseline scores of 0 or 1 unless the corresponding sign score at follow-up visits is >1.
 
The primary efficacy endpoint will be the proportion of subjects with IGA "treatment success" at EOS, where EOS is the subjects last completed post-Baseline visit.
 
Secondary efficacy endpoints (observed data only) include:
 

• The proportion of subjects with IGA "treatment success" at Days 15 and 29.

• The proportion of subjects with a IGA score of 0 or 1 representing "cleared" or "almost cleared" at EOS.

• The proportion of subjects rated "treatment success" for each of the clinical signs and symptoms of IV at Days 15, 29, and EOS.

• Changes in percent BSA with IV in the Treatment Area at Days 15, 29, and EOS relative to Baseline.

• Change from Baseline in 5-D pruritus score at Days 15, 29, and EOS.

• Changes in [REDACTED] at Days 15, 29, and EOS relative to Baseline.

	
Safety Endpoint(s):          Safety endpoints will include assessment of UPT (as applicable), clinical laboratory testing, and AEs, including serious adverse events (SAEs).

Sample Size Calculations
	
No formal power calculations were conducted to establish sample size. The sample size was selected empirically to enable sample size calculations for future pivotal studies.

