
 Subjects with Baseline scores of 0 or 1 will be excluded from summaries and analyses of success rates unless the corresponding sign score at follow-up visits is >1.

	
Safety Analyses:
 
Dosing Compliance Descriptive statistics will be used to summarize test article compliance for the ITT population. Measures of test article compliance will include the duration of treatment (number of days dosed), the total number of applications (determined from the actual number of applications reported by the subject), and the percent of expected doses applied. A subject will be considered compliant with the dosing regimen if the subject applies at least 80% but no more than 120% of the expected number of applications.
 
Extent of Exposure The total amount of test article used (grams of test article applied) will be calculated from the weights of the returned test articles. Descriptive statistics (mean, median, SD, minimum and maximum) will be determined for the total amount of test article used by each subject by treatment group.
 
Clinical Laboratory Testing, and Urine Pregnancy Testing A listing of the clinical laboratory results and UPT results will also be prepared.
 
Adverse Events All AEs reported during the study will be listed, documenting onset, whether therapy was required, any change in test article dosing, severity, possible relationship to test article, and outcome. Verbatim terms on the case report forms (CRFs) will be linked to preferred terms (PTs) and system organ class (SOC) using the Medical Dictionary for Regulatory Activities (MedDRA) mapping system. All reported AEs will be summarized by the number of subjects reporting AEs, SOC, PT, severity, and relationship to test article by treatment group.

--	--

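### Completely clear subjects leave at Day 15 or Day 29, so the per-arm count of subjects with AEs is not an equal-time comparison; add a Day 15 AE table beside it

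*Combined protocol and SAP*

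**What the plan says.** All references are to the Combined protocol and SAP.

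- **Objective (Protocol Synopsis, Study Objective).** "The objective of this study is to determine and compare the safety and efficacy of topical 146-9251 Cream and vehicle cream". Safety is to be compared between the arms, as efficacy is.
- **Early exit (Protocol Synopsis, Study Procedures, Visits 2 and 3).** The rule covers "Subjects whose IV is completely clear (IGA score = 0 and all clinical signs of IV = 0", with scaling, fissuring and erythema as the signs. Such subjects do the end-of-study procedures at Day 15 or Day 29. "These subjects will have completed the study". Subjects who are not clear continue to Visit 4 at Day 43.
- **After exit.** Subjects leave the study at the end-of-study visit (Study Procedures, Visit 4). Note 8 of the Schedule of Events extends follow-up only for treatment-related AEs already ongoing then.
- **AE summary (Statistical Methods, Safety Analyses, Adverse Events).** "All reported AEs will be summarized by the number of subjects reporting AEs, SOC, PT, severity, and relationship to test article by treatment group". AEs are also listed individually with their onset.
- **Exposure (same section).** Days dosed and number of applications are summarised as compliance measures in the ITT population. Extent of exposure is in grams. Neither is linked to the AE table.
- **Size.** "Approximately 88 subjects will be enrolled (44 per treatment arm", randomized 1:1. "No formal power calculations were conducted to establish sample size".

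**The concern.** How long a subject is observed for AEs depends on that subject's efficacy response: about 2 weeks for clearance at Day 15, 4 weeks for clearance at Day 29, and 6 weeks otherwise. If the active cream clears more subjects than vehicle, its arm is observed for less time in total. With the same underlying AE rate in both arms, fewer active subjects will then be counted with an AE.

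The described AE summary has no time denominator, no time-to-onset display and no window common to all subjects. A reader who takes the side-by-side counts as a comparison over equal time would credit the active cream with some tolerability that is only shorter observation. The effect grows with efficacy and weighs most on later-onset reactions. The trial is meant to inform the planning of pivotal studies, so its AE figures are likely to be read again.

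**Working it through.** **The plan's own figures.** Only the sample size can be checked: 88/2 = 44 per arm. The documents give no AE rate, clearance rate or precision target for safety, so the rates below are assumptions.

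**Inputs from the documents.** Observation of 2, 4 or 6 weeks (exit at Day 15, 29 or 43); 44 subjects per arm.

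**Assumptions.** On active, a share *a* clears at Day 15 and a share *b* at Day 29; no vehicle subject clears early. The weekly AE hazard *h* is constant and equal in both arms. Other dropout is ignored.

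**Formulas.** F(t) = 1 − exp(−h·t), t in weeks.

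- Mean follow-up on active = 2a + 4b + 6(1 − a − b)
- Crude AE proportion on active = a·F(2) + b·F(4) + (1 − a − b)·F(6); on vehicle = F(6)
- Gap = a·[F(6) − F(2)] + b·[F(6) − F(4)]
- SE of the difference = √{[p₁(1 − p₁) + p₀(1 − p₀)]/44}

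**At h = 0.05.** F(2) = 9.52%, F(4) = 18.13%, F(6) = 25.92%. For 20%/10% clearing, the gap is 0.20 × 16.40 + 0.10 × 7.79 = 3.28 + 0.78 = 4.06 points.

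| Clear at Day 15 / Day 29 (active) | Mean weeks, active vs vehicle | Crude AE, active vs vehicle | Gap (points) | Gap in subjects of 44 | SE (points) |
|---|---|---|---|---|---|
| 2% / 3% | 5.86 vs 6 | 25.4% vs 25.9% | 0.6 | 0.2 | 9.3 |
| 5% / 5% | 5.7 vs 6 | 24.7% vs 25.9% | 1.2 | 0.5 | 9.3 |
| 10% / 10% | 5.4 vs 6 | 23.5% vs 25.9% | 2.4 | 1.1 | 9.2 |
| 20% / 10% | 5.0 vs 6 | 21.9% vs 25.9% | 4.1 | 1.8 | 9.1 |

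**Other hazards, 20%/10%.** At h = 0.03 the gap is 2.6 points (SE 7.6). At h = 0.10 it is 6.6 points (38.5% vs 45.1%, SE 10.5).

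**Letting vehicle subjects clear too.** Here the assumed six-week AE risk is 30%, again at constant hazard. With 10% + 20% clearing on active against 0 + 5% on vehicle, crude AE is 26.4% vs 29.6%; a true active rate 1.15 times vehicle would give equal crude percentages. In a deliberately extreme case (30% + 30% against 5% + 5%) the figures are 21.7% vs 28.6% and 1.39 times.

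**Does a common window remove it?** No clear exit can occur before the Day 15 visit. With the same hazard, both arms have expected incidence F(2) at that visit, and the expected difference is 0.

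**Does a person-time rate remove it?** Only if the hazard is roughly constant. Take a six-week risk of 30% and 20%/10% clearing, with early-loaded AEs: F(t) = 1 − exp[−H(t/42)^0.5], t in days, H = −ln 0.70 = 0.357.

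- F(14) = 18.6%, F(28) = 25.3%, F(42) = 30.0%.
- Crude active = 0.2 × 18.6 + 0.1 × 25.3 + 0.7 × 30.0 = 27.2%; ratio to vehicle 27.2/30.0 = 0.91.
- Rate ratio on total follow-up time = 0.908/(5/6) = 1.09; with time censored at first AE, 1.08.

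The true ratio is 1.00, so the rate errs about as much as the crude count, in the other direction. With a constant hazard, censoring at first AE gives exactly 1.00; using total time to last visit gives 1.01.

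**The case against.** Several points on the other side stand.

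- **The crude count answers a real question.** The regimen under test is treatment for up to six weeks, ending at complete clearance. Fewer AEs because of less exposure is a genuine consequence of that regimen. A reader might infer that the planned table is biased or invalid; the documents do not support that. It misleads only if taken as an equal-time rate, and nothing in the text says it will be.
- **No AE test is planned.** There is no AE test, interval or safety hypothesis, only descriptive tables by arm. A reader might infer that the trial is set to declare the active cream safer; it is not.
- **Complete clearance may be rare.** It requires IGA 0 and all three signs 0 within two or four weeks, from a baseline IGA of at least 3. If few subjects get there, the gap is under 1 point.
- **The gap is within noise** in every scenario tried. That limits its practical weight, although it has a consistent direction that sampling error does not remove.
- **Early-loaded AEs shrink it, and other dropout could offset it.** Discontinuation in either arm also shortens follow-up, and the calculation leaves it out.
- **Unequal exposure would be partly visible** from days dosed and grams used, and AE onset is listed. But those summaries do not give a corrected AE comparison, and days dosed is reported for the ITT rather than the Safety population.
- **The text is a synopsis.** It refers to a statistical analysis plan for per-protocol details, and a fuller text could contain an additional AE table. None is described here.

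**Conclusion.** The point holds in a limited form. Length of AE observation depends on response, new AEs after early exit are not captured, and the only AE summary described counts subjects per arm. If the active cream clears more subjects, that summary tilts towards it when read as an equal-time comparison, which the stated objective of comparing safety invites.

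Under the main assumptions (5% to 30% of active and no vehicle subjects clearing early, equal constant hazard of 0.05 per week) the tilt is 0.6 to 4.1 points, against a standard error of about 9. The real size cannot be known from the documents. This is a reporting gap worth closing in a Phase 2 trial without a formal safety hypothesis; it does not invalidate the safety analysis.

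A reader might also conclude that exposure-adjusted rates should replace the crude table or carry the safety conclusion. The early-loaded example shows why not: the rate then errs against the active arm by about as much as the crude count errs in its favour.

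**What to change.** In Statistical Methods, Safety Analyses, Adverse Events, keep the crude table and label it as the summary under treatment until clearance. Add, for the Safety population by arm:

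1. The number and percentage of subjects with AE onset from first application up to the Day 15 visit, overall and treatment-related, named as the equal-follow-up comparison.
2. Subject-time on study, from first application to last visit.

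An exposure-adjusted first-AE rate, with each subject's time censored at the first AE, may be shown as supportive only. It should carry a note that it assumes a roughly constant hazard and can err against the active arm if AEs occur early. Specify all of this before unblinding.

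The cost is one or two extra tables from dates the trial already needs (supervised first application, AE onset, last visit). Visits and procedures do not change. The limitation is that the Day 15 window says nothing about later-onset AEs, and subjects lost before that visit for other reasons still have shorter follow-up. The crude table and the subject-time must therefore be read alongside it.

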## SCHEDULE OF EVENTS

Study Day	Visit 1 Screening/ Baseline  Day 1	Visit 2 Week 2 Day 15 (±2)	Visit 3 Week 4 Day 29 (±2)	Visit 4 Week 6 EOT/EOS Day 43 (±3) 
Informed Consent/Assent	X			
Inclusion/Exclusion Criteria	X 			
Urine Pregnancy Testing  for WOCBP 	X 			X 
Medical History/Demographics	X			
Brief Physical Exam	X			
Vital Signs, Height, & Weight	X			
Clinical Evaluations (IGA, Clinical Signs of IV, ██████, Pruritus)	X  (prior to test article application)	X	X	X
Record percent BSA with IV in the Treatment Area	X	X	X	X
Randomization to Treatment Regimen (Subject # Assignment)	X			
Provide (or review) Instruction Sheet to Subject & Parent/Guardian (if applicable) and Demonstrate How to Apply the Test Article 	X	X	X	
Provide Subject Diary to Subject & Parent/Guardian (if applicable) and Completion Instructions	X			
Clinical Laboratory Assessments	X 			X 
Photography (Select Sites)	X	X	X	X
Review/Dispense/ Collect Subject Diary		X	X	X
Weigh/Dispense Test Articles	X	X	X	
Weigh/Collect Test Articles		X	X	X
Instruct Subject to Continue Twice Daily Treatment	X	X	X	
Record Concomitant Medications and Procedures/Therapies	X	X	X	X
Record Adverse Events	X	X	X	X 

1. Screening assessment may be performed up to 45 days prior to the Baseline Visit for those qualified subjects that are eligible to enroll in the study but require wash-out of medications prior to enrolling into the treatment phase of the study. Screening and Baseline activities may be combined into a single visit if the subject does not require washout.
2. This activity may occur at an earlier visit if the subject is discontinued from the study.
3. For those subjects that required a washout period related to exclusionary medications, need to reaffirm these subjects meet all protocol requirements at the Baseline Visit.
4. UPTs must have a minimum sensitivity of 25 mIU β-hCG/mL of urine.
5. WOCBP include any female who has experienced menarche or is 10 years of age or older and who has not undergone successful surgical sterilization (hysterectomy, bilateral tubal ligation (within six months of initiation of treatment), or bilateral oophorectomy) or is not postmenopausal (defined as amenorrhea >12 consecutive months in women 50 years of age and older).
6. See application guidelines per protocol and in the subject instruction sheet.
7. Perform laboratory tests (blood chemistries, hematology, and urinalysis).
8. Any treatment related AEs that are ongoing at EOS must be followed until resolution or stabilization.

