 1% BSA is approximately equal to the surface area of the subject's palm and fingers, with the fingers extended yet grouped together, creating a flat oval-like surface area.

	

5. Subject has an Investigator's Global Assessment (IGA) score of at least three (3 = moderate) at the Baseline Visit.

6. Subject is in good general health and free of any disease state or physical condition that might impair evaluation of IV or which, in the investigator's opinion, exposes the subject to an unacceptable risk by study participation.

7. Females must be post-menopausal, surgically sterile, or use an effective method of birth control. Women of childbearing potential (WOCBP) must have a negative urine pregnancy test (UPT) at the Baseline Visit.

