Exclusion Criteria	
A subject is ineligible to enter the study if he/she meets one or more of the following criteria:
 

1. Subject is pregnant, lactating, or is planning to become pregnant during the study.

2. Subject is currently enrolled in an investigational drug or device study.

3. Subject has used an investigational drug or investigational device treatment within 30 days prior to first application of the test article.

4. Subject has used any topical therapy, including urea products, topical corticosteroids, or retinoids, in the Treatment Area within 2 weeks prior to the initiation of treatment. Note: a bland emollient may be used in the Treatment Area up to 3 days prior to the initiation of treatment.

5. Subject has used systemic corticosteroids within 4 weeks or retinoids within 24 weeks prior to the initiation of treatment.

6. Subject has stable use of vitamin or herbal supplements for less than 2 weeks prior to the initiation of treatment.

7. Subject has a history of sensitivity to any of the ingredients in the test articles.

8. Subject is known to be noncompliant or is unlikely to comply with the requirements of the study protocol (e.g., due to alcoholism, drug dependency, mental incapacity) in the opinion of the investigator.

9. Subject has a physical condition or other dermatologic disorders (e.g., atopic, seborrheic or contact dermatitis, psoriasis, tinea infections, etc.) which, in the investigator's opinion, might impair evaluation of IV, or which exposes the subject to unacceptable risk by study participation.

Study Procedures	
Subjects can be screened for the study up to 45 days before Visit 1. During screening, the study requirements will be reviewed, written informed consent/assent obtained, and eligibility confirmed. If applicable, the washout from prohibited medications or treatments will be determined and implemented. These procedures may be combined with the Baseline Visit if medication washout is not required. The following procedures will take place according to the visit schedule:

 Defined as amenorrhea greater than 12 consecutive months in women 50 years of age and older.

 Hysterectomy, bilateral tubal ligation (at least six months prior to initiation of treatment), or bilateral oophorectomy.

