 Effective forms of birth control include a) hormonal contraceptives [e.g., oral, transdermal, injectable, or vaginal ring] (see footnote 5), b) intrauterine device (IUD) for at least one week prior to test article application, c) barrier methods [condom and spermicidal or diaphragm/cervical cap and spermicidal], d) monogamous relationship with a partner who is sterile [e.g., vasectomy performed at least six months prior to study entry], or e) total abstinence for subjects who are not sexually active. Subjects who become sexually active or begin to have relations with a partner who is not sterile during the study must agree to use an effective form of birth control for the duration of the study.

 WOCBP taking hormonal therapy must be on treatment prior to study entry, continued per label, and must not change their dosing regimen during the study; treatment must be for (1) oral: at least one complete cycle (e.g., four to eight weeks); (2) transdermal, injectable (e.g., Depo-Provera), or vaginal ring (e.g., NuvaRing): at least one week.

 UPT must have a minimum sensitivity of 25 mIU  $\beta$ -hCG/mL.

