--	---

	
with IV in the Treatment Area, perform clinical laboratory testing, perform photography, which is optional, at select site(s) per a photo guide provided by the Sponsor, update concomitant medications and procedures/therapies, record AEs, collect and review the Subject Diary for test article compliance and collect and weigh used test article. A UPT will be performed on all WOCBP. All subjects will exit the study.

Study Measurements	
At each visit, the skin affected with IV in the Treatment Area defined at the Baseline Visit will be assessed as follows:
 
Efficacy: Investigator’s Global Assessment The IGA score is a static evaluation of the overall or “average” degree of severity of a subject’s disease, taking into account all of the subject’s scaling, erythema, and fissuring in the Treatment Area by the investigator or designee as the subject appears on the day of the evaluation. This evaluation takes into consideration the three individual characteristics of IV (scaling, fissuring, and erythema) as well as hyperpigmentation with the IGA score at each visit representing the average degree of scaling, fissuring, and erythema (<math>\pm</math> hyperpigmentation, if present) that is eligible for treatment. IGA will be assessed using the following 5-point scale: clear (0), almost clear (1), mild (2), moderate (3), or severe (4).
 
Clinical Signs of Ichthyosis Vulgaris Scaling, fissuring, and erythema in the Treatment Area will be graded using the following 5-point scale: clear (0), almost clear (1), mild (2), moderate (3), or severe (4).
 
The degree of hyperpigmentation relative to the subject’s normal skin color associated with the disease affected skin in the Treatment Area will be graded using the following 5-point scale: none (0), minimal (1), mild (2), moderate (3), or severe (4).
 
[REDACTED]
 
[REDACTED]
 
[REDACTED]
 
[REDACTED]
 
[REDACTED]

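### Schedule of Events footnote 5 reverses the Synopsis six-month rule for tubal ligation, so a recently ligated woman can miss both pregnancy tests

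*Combined protocol and SAP*

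**What the plan says.** Inclusion criterion 7 (Protocol Synopsis) admits females who are post-menopausal, surgically sterile or using effective birth control, and adds: "Women of childbearing potential (WOCBP) must have a negative urine pregnancy test" at Baseline. Synopsis footnote 3 defines surgically sterile: "Hysterectomy, bilateral tubal ligation (at least six months prior to initiation of treatment), or bilateral oophorectomy". Synopsis footnote 4 applies a lag in the same direction to a sterile partner: "vasectomy performed at least six months prior to study entry".

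The Schedule of Events marks the UPT at Visit 1 and at Visit 4 (end of study, EOS), for WOCBP only. The Visit 4 text in Study Procedures repeats this: "A UPT will be performed on all WOCBP". Footnote 5 to that row is the only explicit definition of WOCBP in the supplied text. It covers a female past menarche or aged 10 or over "who has not undergone successful surgical sterilization", and it lists as sterilisation hysterectomy, oophorectomy and "bilateral tubal ligation (within six months of initiation of treatment"). It then continues "or is not postmenopausal (defined as amenorrhea" of more than 12 months at age 50 or over).

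The Schedule has its own footnote 3, on washout. Below, footnote 3 always means the Synopsis footnote.

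**The concern.** The two footnotes should draw the same line, because one decides who counts as sterile for eligibility and the other decides who is tested. They draw opposite lines. Footnote 3 treats a ligation as effective once six months have passed; Schedule footnote 5 treats it as effective only while six months have not passed. Exempting a recent ligation but not an old one has no evident rationale, and the vasectomy rule in footnote 4 agrees with footnote 3, so footnote 5 looks like a drafting slip.

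What is at stake is a safeguard. The Baseline UPT is the only pregnancy test scheduled before dosing with an investigational cream, which is applied twice daily for up to 6 weeks. A woman whom criterion 7 regards as not yet sterile could start treatment without that test and leave the study without the EOS test.

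**Working it through.** The documents give no figure to reproduce, so the check sets the definitions side by side and counts scheduled tests.

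**Inputs**

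- UPT occasions for a WOCBP: Visit 1 and Visit 4, so 1 + 1 = 2 (Schedule of Events, UPT row). For a woman who is not a WOCBP: 0.
- Woman considered: not postmenopausal, with tubal ligation as her only sterilising procedure, done *m* months before treatment. Women who are postmenopausal, or who also had a hysterectomy or bilateral oophorectomy, are outside the point.

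**Rules**

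- Footnote 3: sterile if *m* ≥ 6. Tests = 0 if *m* ≥ 6, otherwise 2.
- Schedule footnote 5, ordinary reading (a WOCBP is neither sterilised nor postmenopausal): sterilised if *m* ≤ 6. Tests = 0 if *m* ≤ 6, otherwise 2.
- Schedule footnote 5, literal reading of the conjunction: not being postmenopausal is enough to be a WOCBP. Tests = 2 for every *m*.

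**Tests scheduled per woman**

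| Ligation before treatment | Footnote 3 rule | Schedule fn 5, ordinary reading | Schedule fn 5, literal reading |
|---|---|---|---|
| 1 month | 2 | 0 | 2 |
| 5.9 months | 2 | 0 | 2 |
| exactly 6 months | 0 | 0 | 2 |
| 6.1 months | 0 | 2 | 2 |
| 24 months | 0 | 2 | 2 |

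On the ordinary reading, Schedule footnote 5 schedules 2 tests too few below six months and 2 too many above. On the literal reading it schedules none too few, and 2 too many from six months onward. The literal reading also gives the sterilisation clause no effect for any woman who is not postmenopausal: even one who has had a hysterectomy would be tested. Neither reading reproduces footnote 3.

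**Check of the correction**

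With footnote 3's timing in Schedule footnote 5 and the two conditions joined by *and*:

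- Ligation 3 months earlier: not sterilised, not postmenopausal, therefore WOCBP, 2 tests. Footnote 3 gives 2.
- Ligation 12 months earlier: sterilised, therefore not WOCBP, 0 tests. Footnote 3 gives 0.

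Both edits are needed. Changing only the timing leaves the 2 unnecessary tests on a literal reading. Changing only the conjunction makes the 0-test result for recent ligation the plain meaning.

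**The case against.** The strongest reply is that a missed test requires a mixed reading. Taken literally throughout, footnote 5 makes every woman who is not postmenopausal a WOCBP, and she is tested. With both slips silently repaired, she is tested too. The gap appears only when the conjunction is read sensibly and the timing phrase is read as printed. Further, the footnote says whom WOCBP include, which need not be an exhaustive list. Criterion 7 read alone suggests that WOCBP are the women who are neither post-menopausal nor sterile under footnote 3, which would put a recently ligated woman in the Baseline test. Contraception is never waived, exclusion 1 bars pregnant women, extra tests for older ligations harm no one, and few women can be concerned. Fuller protocol text might also define WOCBP elsewhere.

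Much of this stands as a limit on the consequence: the missed test is a possible result, not a certain one, and the statement about the only definition applies to the supplied text. It does not remove the conflict. Neither sterilised nor postmenopausal is how most readers would take the footnote, and that is the reading under which the tests drop out. A site might instead take the six-month phrase as a carve-out for ligations that do not yet count. With about 5 sites, that invites different practice on the same rule. Exclusion 1 is weaker protection if an unrecognised pregnancy is never tested for.

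**Conclusion.** The concern holds. Schedule footnote 5 contradicts the sterility rule behind criterion 7, and no reading of it as printed agrees with that rule.

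The size per woman is 2 scheduled UPTs: 2 omitted after a recent ligation on the ordinary reading, or 2 unnecessary after a ligation more than six months old on either reading. This assumes that footnote 3 states the intended direction, which footnote 4 supports. How many of the approximately 88 subjects fall into either group cannot be derived from the documents.

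The safety gap is confined to missed tests. UPT is a named safety endpoint, but its results are only listed, so no efficacy analysis or comparison is affected. This is an inconsistency that should be corrected, not one that threatens the trial's conclusions.

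**What to change.** In Schedule of Events footnote 5, replace the six-month phrase with the Synopsis footnote 3 wording, so that the entry reads "bilateral tubal ligation (at least six months prior to initiation of treatment"). In the same edit, change the word joining the sterilisation and postmenopausal conditions from *or* to *and*. One definition then governs both eligibility and UPT scheduling.

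The cost is one phrase and one conjunction in a protocol amendment, plus a clarification to sites. There are no added visits and no change to any analysis. Relative to the ordinary reading of the current text, a recently ligated woman gains two urine tests and a woman with an older ligation loses two.
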